7. PLANNED ANALYSIS

Safety analysis (refer to [Section 7.8](#)) will be performed by and will be presented in Sections 15.1 to 15.4 of the CTR and in Appendix 16.2 and 16.1.13.1.

Inferential statistical analyses of PK endpoints (refer to [Section 7.4](#) and [Section 7.5.2](#)) will also be performed by and will be presented in Section 15.5 of the CTR and in Appendix 16.1.13.3.

Descriptive data analysis of PK parameters and concentrations will be performed by BI and presented in Section 15.6 of the CTR.

The format of the listings and tables will follow the standards defined in the BI corporate guideline “Reporting of Clinical Trials and Project Summaries” [001-MCG-159] ([6](#)) with the exception of those generated for PK-calculations.

The individual values of all subjects will be listed, sorted by treatment, subject number and visit. The listings will be included in Appendix 16.2 of the CTR.

For end-of-text tables, the set of summary statistics for non-PK parameters is:

N	number non-missing observations
Mean	arithmetic mean
SD	standard deviation
Min	minimum
Median	median
Max	maximum

For analyte concentrations as well as for all PK parameters, the following descriptive statistics will additionally be calculated:

CV	arithmetic coefficient of variation
gMean	geometric mean
gCV	geometric coefficient of variation

The descriptive statistics of PK parameters will be calculated using the individual values with the number of decimal places as provided by the evaluation program. Then the individual values as well as the descriptive statistics will be reported with three significant digits in the CTR.

Tabulations of frequencies for categorical data will include all possible categories and will display the number of observations in a category, as well as the percentage (%) for each treatment group. Percentages will be rounded to one decimal place and will be based on all subjects in the respective subject set whether they have non-missing values or not. The category 'missing' will be displayed only if there are actually missing values.

Units of variables should be given in the titles or column/row descriptors in square brackets (e.g. [mg]).

Exclusion of PK parameters

The ADS ADPP (PK parameters) contains column variables APEXC and APEXCO indicating inclusion/exclusion (APEXC) of a PK parameter and an analysis flag comment (APEXCO). All analyses based on the PKS will include parameters if they are not flagged for exclusion, that is APEXCO is equal to “Included”.

Exclusion of PK concentrations

The ADS ADPC (PK concentrations per time-point or per time-interval) contains column variables ACEXC or ACEXCO indicating inclusion/exclusion (ACEXC) of a concentration and an analysis flag comment (ACEXCO). Exclusion of a concentration depends on the analysis flag comment ACEXCO. For example, if ACEXCO is set to ‘ALL CALC’, the value will be excluded for all types of analyses based on concentrations. If ACEXCO is set to ‘DESC STATS’ the value will be excluded from descriptive evaluations per planned time point/time interval. If ACEXCO contains the addition ‘TIME VIOLATION’ or ‘TIME DEVIATION’ the value can be used for further analyses based on actual times. If ACEXCO is set to ‘HALF LIFE’ the value will be excluded from half-life calculation (and, as a consequence, any calculation that relies on λ_z) only; the value is included for all other analyses.

Further details are given in 001-MCS-36-472_RD-01 “Noncompartmental Pharmacokinetic / Pharmacodynamic Analyses of Clinical Studies” ([5](#)) and 001-MCS-36-472_RD-03 “Description of Analytical Transfer Files and PK/PD Data Files” ([11](#)).

7.1 DEMOGRAPHIC AND OTHER BASELINE CHARACTERISTICS

Only descriptive statistics are planned for this section of the report, based on the TS.

The data will be summarised for both formulations together (BI tab + iv).

7.2 CONCOMITANT DISEASES AND MEDICATION

Frequency tables are planned for this section of the report, based on the TS.

Concomitant diseases will be coded using the coding system of the Medical Dictionary for Drug Regulatory Activities (MedDRA). Medications will be coded using the World Health Organization Drug Dictionary (WHO-DD). The coding version number will be displayed as a footnote in the respective output.

The diagnoses and medications will be listed. Subjects without any concomitant diagnoses or concomitant therapies should be marked with a “No” in the respective column.

The relevance of the concomitant therapies to the evaluation of PK will be decided no later than at the RPM/DBLM.

7.3 TREATMENT COMPLIANCE

Section 4.3 of the CTP: *Compliance will be assured by administration of all trial medication in the study centre under supervision of the investigating physician or a designee. The measured plasma concentrations and/or urinary excretion will provide additional confirmation of compliance.*

It is not intended to list the compliance separately. Any deviations from complete intake will be addressed in the RPM/DBLM (cf. TSAP [Section 6.2](#)) and described in the CTR.

7.4 PRIMARY ENDPOINTS

Absolute bioavailability is to be determined on the basis of the dose normalized primary pharmacokinetic endpoints (see [Section 5.1](#)).

Primary analysis

The statistical model used for the analysis of the primary endpoints will be an ANOVA (analysis of variance) model on the logarithmic scale. This model will include effects accounting for the following sources of variation: 'subjects' and 'formulation'. The effect 'subjects' will be considered as random, whereas 'formulation' will be considered as fixed.

The model is described by the following equation:

$y_{km} = \mu + s_m + \tau_k + e_{km}$, where

y_{km} = logarithm of response (dose normalized primary endpoint, see [Section 5.1](#)) measured on subject m receiving formulation k ,

μ = the overall mean,

s_m = the effect associated with the m^{th} subject $m = 1, 2, \dots, n$

τ_k = the k^{th} formulation effect (either tablet or i.v.), $k = 1, 2$,

e_{km} = the random error associated with the m^{th} subject who received formulation k .

The implementation for this analysis will be accomplished by using the XPKISTAT macro, based on PKS, and option BWU (Bioavailability/Bioequivalence, within-subject design, uncontrolled w.r.t. time).

Section 7.3.1 of the CTP: [...] the dose normalized PK endpoints will be log transformed (natural logarithm) prior to fitting the ANOVA model [...] For each endpoint, the difference

between the expected means for $\log(T)$ - $\log(R)$, will be estimated by the difference in the corresponding adjusted means (Least Squares Means), and a two-sided 90% confidence interval (CI) based on the t-distribution will be computed. These quantities will then be back-transformed to the original scale to provide the point estimate and 90% CIs for each endpoint.

The response variables used in the ANOVA model are the following:

for C_{max} : $C_{max, norm, po}$ and $C_{max, norm, iv}$

for AUC: $AUC_{0-\infty, norm, po}$ and $AUC_{0-\infty, norm, iv}$

Further analysis

Section 7.3.2 of the CTP: *As a sensitivity analysis, the ANOVA performed as primary analysis will be repeated with subject as fixed effect instead of random effect. The results will be presented in the same manner as for the primary analyses.*

Furthermore, the input dataset will be restricted in such a way that treatments not relevant for the comparison of interest will be deleted. This analysis will be done using PROC GLM.

The following SAS code can be used to fit the model:

```
PROC GLM DATA=indata;
  CLASS subject treatment;
  MODEL logkp = treatment subject;
  LSMEANS treatment / PDIFF=CONTROL("Ref_trt") CL ALPHA=0.1;
  RUN;
```

Section 7.3.2 of the CTP: *If an adequate number of PM subjects is reached within the study a subgroup analysis will be done for the primary PK endpoints to compare PM subjects with non-PM subjects.*

This subgroup analysis will be done using the same model and parameters as for the primary analysis but including the PM status as a covariate (fixed effect).

The implementation for this analysis will be accomplished by using the XPKISTAT macro, based on PKS, option BWU (Bioavailability/Bioequivalence, within-subject design, uncontrolled w.r.t. time), and CLASSFIX=PM status.

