3.3 SELECTION OF TRIAL POPULATION

It is planned that up to 12 healthy male and female subjects will enter the study. They will be recruited from the volunteers' pool of the trial site.

To explore potential differences in absolute bioavailability based on 2C19 metabolizer status, it is planned to include 6 subjects with CYP2C19 non-PM status, and up to 6 subjects with 2C19 PM status, if feasible.

A log of all subjects enrolled into the trial (i.e. having given informed consent) will be maintained in the ISF at the investigational site irrespective of whether they have been treated with investigational drug or not.

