5.5.1.2 Secondary endpoints

The following secondary endpoints will be evaluated.

For BI 409306 and BI 409306 (C-13/N-15):

Proprietary confidential information © 2018 Boehringer Ingelheim International GmbH or one or more of its affiliated companies

- $t_{1/2}$ (terminal half-life of the analyte in plasma)
- t_{max} (time from dosing to maximum measured concentration of the analyte in plasma)

For BI 409306 (C-13/N-15):

- CL (total clearance of the analyte)
- V_z (Apparent volume of distribution during the terminal phase after intravascular administration)

For BI 409306

- F (absolute bioavailability)

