7.2 NULL AND ALTERNATIVE HYPOTHESES

The absolute bioavailability of 50 mg of orally administered unlabeled BI 409306 compared to 0.1 mg intravenously administered stable labeled isotope BI 409306 (C-13/N-15) will be estimated by the ratios of the geometric means (test/reference) for the dose normalized primary PK endpoints. Additionally, their two-sided 90% confidence interval (CI) will be provided. This method corresponds to the two one-sided t-tests procedure, each at the 5% significance level. Since the main focus is on estimation and not testing, an acceptance range was not specified, that is, no hypothesis will be tested.

Confidence intervals and p-values will be computed, but have to be interpreted in the perspective of the exploratory character of the study, i.e. confidence intervals are considered as interval estimates for effects, while p-values are considered as an exploratory measure of evidence for effects in the present data.

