7.3.2 Secondary analyses

As a sensitivity analysis, the ANOVA performed as primary analysis will be repeated with subject as fixed effect instead of random effect. The results will be presented in the same manner as for the primary analyses.

If an adequate number of PM subjects is reached within the study a subgroup analysis will be done for the primary PK endpoints to compare PM subjects with non-PM subjects.

The following descriptive statistics will be calculated for primary and secondary PK parameters and for further endpoints: N, arithmetic mean, standard deviation, minimum, median, maximum, arithmetic coefficient of variation, geometric mean, and geometric coefficient of variation. The data format for descriptive statistics of concentrations will be identical with the data format of the respective concentrations. The descriptive statistics of PK parameters will be calculated using the individual values with the number of decimal places as provided by the evaluation program. Then the individual values as well as the descriptive statistics will be reported with 3 significant digits in the clinical trial report.

The secondary parameters (refer to Section [5.5.1.2](#)) will be calculated according to the BI SOP 'Standards and processes for analyses performed within Clinical Pharmacokinetics/ Pharmacodynamics' ([001-MCS-36-472](#)).

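### The CYP2C19 subgroup model in SAP 7.4 has no formulation-by-status term, so it assumes one T/R ratio and cannot estimate a PM versus non-PM difference in absolute bioavailability

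*SAP*

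**What the plan says.** Protocol 3.3 gives the reason for recruiting both genotype groups: "To explore potential differences in absolute bioavailability based on 2C19 metabolizer status". It plans 6 non-PM and up to 6 PM subjects. Protocol 7.2 takes absolute bioavailability to be the test/reference ratio of geometric means of the dose-normalised primary endpoints, which is the formulation contrast on the log scale.

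If enough PM subjects are recruited, Protocol 7.3.2 states that "a subgroup analysis will be done for the primary PK endpoints to compare PM subjects with non-PM subjects".

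The primary model in SAP 7.4 has one formulation effect and a subject effect: "The effect 'subjects' will be considered as random, whereas 'formulation' will be considered as fixed". For the T/R contrast, "a two-sided 90% confidence interval (CI) based on the t-distribution will be computed". The subgroup analysis is then defined as "using the same model and parameters as for the primary analysis but including the PM status as a covariate (fixed effect", run with the XPKISTAT macro using the option described as "within-subject design, uncontrolled w.r.t. time), and CLASSFIX=PM status". Neither the prose nor the macro call mentions a formulation-by-status term, a separate fit by status, or T/R by status.

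Protocol 5.5.1.2 lists "F (absolute bioavailability" as a secondary endpoint, and Protocol 7.3.2 plans descriptive statistics for it. The available text states no split by status.

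**The concern.** If bioavailability is the T/R ratio, a difference in bioavailability by genotype is a difference in T/R by genotype, which is an interaction between formulation and status. A model with only a main effect of status fixes that interaction at zero. It assumes away the effect that the two groups were recruited to explore.

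In the available text this is the only model-based comparison by status. Followed as written, it gives no F within PM, no F within non-PM, and no interval for the ratio of the two. A reader could also mistake the PM coefficient, which is an exposure difference, for a difference in bioavailability.

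**Working it through.** The documents give no variance, effect size or precision target, so there is no planned figure to reproduce. The number of subjects (6 + up to 6), the model and the 90% level come from the documents. The values of F, clearance (CL), SD and CV below are assumptions.

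**1. Algebra.** The model as worded is y = μ + s_m + τ_k + β·PM_m + e_km. For each subject,

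D = log T − log R = (τ_T − τ_R) + (e_T − e_R).

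Both s_m and β·PM_m cancel. With complete pairs, T/R = exp(mean D), with or without the PM term.

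The PM coefficient is the group difference in log exposure averaged over the two routes. For dose-normalised AUC the i.v. difference is log(1/CL ratio) and the oral difference is log(1/CL ratio) + log(F ratio). Hence

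β = log(1/CL ratio) + 0.5·log(F ratio),

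which is not the log of the F ratio.

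**2. Noise-free example.** Take F = 0.30 (non-PM) and 0.80 (PM), 2-fold higher i.v. exposure in PM, and 6 + 6 subjects. The additive model returns one F of √(0.30 × 0.80) = 0.49 and a PM effect of 2 × √(0.80/0.30) = 3.27. The true ratio of F is 0.80/0.30 = 2.67, which the interaction model recovers.

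**3. Different F ratios, same planned estimates.** The CL ratio is set to √(F ratio)/2^1.5 so that β is the same in every scenario. This shows non-identifiability, not a likely size of error. Residual SD is 0.2 and all pairs are complete.

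| F non-PM / PM | F ratio | CL ratio | i.v. exposure ratio | oral exposure ratio | T/R from plan | PM effect from plan |
|---|---|---|---|---|---|---|
| 0.566 / 0.566 | 1.0 | 0.354 | 2.83 | 2.83 | 0.566 | 2.83 |
| 0.462 / 0.693 | 1.5 | 0.433 | 2.31 | 3.46 | 0.566 | 2.83 |
| 0.40 / 0.80 | 2.0 | 0.500 | 2.00 | 4.00 | 0.566 | 2.83 |

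**4. Where the difference goes.** With d = log(F ratio), the expected variance of D under one common ratio is 2·SD² + d²·n₁n₂/[n(n − 1)]. Here 2·SD² = 0.08 and n₁n₂/[n(n − 1)] = 36/132.

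- F ratio 1.0: 0.080, which is 1.00 times baseline.
- F ratio 1.5: 0.080 + 0.405² × 36/132 = 0.125, which is 1.56 times.
- F ratio 2.0: 0.080 + 0.693² × 36/132 = 0.211, which is 2.64 times.

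The 90% CI factor for T/R (divide and multiply) is exp(t(0.95, 11)·√(var/12)), with t = 1.796: 1.16, 1.20 and 1.27. Equal F with residual SD 0.200, 0.250 or 0.325 gives the same three factors, so a wider interval does not reveal a difference in F.

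**5. Simulation check.** 200 trials per scenario, between-subject SD 0.3, REML fits. T/R with and without the PM term differed by less than 1e-15. Means for the three scenarios were T/R 0.569, 0.564, 0.567; PM effect 2.80, 2.87, 2.86; residual variance 0.99, 1.56, 2.59 times 0.04. The formulation × status term gave 0.99, 1.53 and 2.00.

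**6. Precision with the interaction.** The 90% CI factor for the PM/non-PM ratio of F is exp(t(0.95, 6 + n_PM − 2)·√(2·ln(1 + CV²)·(1/6 + 1/n_PM))).

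| Intra-subject CV | 6 vs 6 | 6 vs 3 | 6 vs 2 |
|---|---|---|---|
| 10% | 1.16 | 1.21 | 1.25 |
| 20% | 1.34 | 1.46 | 1.56 |
| 30% | 1.54 | 1.74 | 1.93 |
| 40% | 1.77 | 2.07 | 2.37 |

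**The case against.** The strongest reply is that the SAP delivers what Protocol 7.3.2 promises. The primary endpoints are AUC and C_max, F is listed separately, and a PM main effect on dose-normalised AUC and C_max is literally a comparison of PM with non-PM subjects. No CYP2C19 objective appears in Protocol 7.1.1, the analysis depends on an undefined adequate number of PM subjects, and Protocol 7.2 says: "Confidence intervals and p-values will be computed, but have to be interpreted in the perspective of the exploratory character of the study". Individual PK values and CYP2C19 results will be reported, so anyone could compute F by status afterwards. CLASSFIX is not defined in the documents, and the macro may print more than the prose implies.

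Much of this stands, and it limits the consequence. The PM coefficient does compare exposure, though averaged over two routes and so describing neither. An informal comparison of F will be possible. What the macro prints is unknown.

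It does not remove the mismatch. The stated reason for having two groups is bioavailability, which the protocol derives from T/R, and the written model allows only one T/R. Protocol 7.2 treats confidence intervals as the interval estimates of effects; for this effect the SAP specifies none. If CLASSFIX does more than add a main effect, the SAP should say so.

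A further caution concerns the remedy. With very few PM subjects, T/R within PM relies on a residual variance pooled across groups. At CV 20% and 2 PM subjects the pooled factor is 1.47. Fitting those two subjects alone, with 1 degree of freedom, gives about 3.49.

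**Conclusion.** The concern holds for the specification as written. With complete pairs, the subgroup model returns the primary T/R estimate again together with a route-averaged exposure difference; it gives neither F by status nor the ratio of F. The cancellation is algebraic and does not depend on the assumed values. The scenarios only illustrate it: F ratios from 1.0 to 2.0 can share identical planned point estimates.

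This should be fixed, but its reach is limited to an exploratory, conditional analysis. The pooled primary estimate and its interval come from a separate model and are unaffected. The conclusion does not cover undocumented macro behaviour or SAP and protocol text that was not available.

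**What to change.** In SAP 7.4, specify the subgroup model with fixed effects for formulation, PM status and formulation × PM status, and a random subject effect. Report:

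- T/R with 90% CI within non-PM and within PM;
- for AUC, the PM/non-PM ratio of F with 90% CI, from the interaction term;
- if exposure by status is also wanted, the PM/non-PM comparison separately for oral and i.v.

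Confirm that the XPKISTAT call fits this model, or give explicit mixed-model code. State that the residual variance is pooled across status groups.

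The cost is SAP wording and one model term, with no new data or subjects. The drawback is a wide exploratory interval for the ratio of F: a factor of 1.16 to 1.77 for 6 versus 6 at assumed CVs of 10% to 40%, and up to 2.37 with 2 PM subjects. At CV 20% the within-status T/R factor is exp(t(0.95, 6 + n_PM − 2)·√(2·ln(1 + CV²)/n)), with n the size of that group. This gives 1.23 in each group for 6 versus 6, and 1.25 (non-PM) and 1.47 (PM) for 6 versus 2.

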7.5 SECONDARY ENDPOINTS

7.5.1 Key secondary endpoints

This section is not applicable as no key secondary endpoint has been specified in the protocol.

7.5.2 Secondary endpoints

Descriptive statistics of plasma concentrations and PK endpoints will be done by department Translational Medicine and Clinical Pharmacology at BI and will be presented in Section 15.6 of the CTR.

The analysis of PK parameters as well as the tables and graphs for the pharmacokinetic non-compartmental analyses will follow specific definitions of this TSAP or, otherwise, the BI standard procedure “Standards and processes for analyses performed within Clinical Pharmacokinetics/Pharmacodynamics” [001-MCS-36-472] ([7](#)).

7.7 EXTENT OF EXPOSURE

Descriptive statistics are planned for this section of the report based on the TS. The date and time of drug administration will be listed for each subject.

7.8 SAFETY ANALYSIS

All safety analyses will be performed on the TS.

The safety data for treated subjects who failed to complete the study (dropouts or withdrawals) will be reported as far as their data are available. All withdrawals will be documented and the reason for withdrawal recorded.

7.8.1 Adverse events

AEs will be coded with the most recent version of MedDRA.

The analyses of AEs will be descriptive in nature and will be based on BI standards as presented in the corporate guideline: “Analysis and Presentation of Adverse Event Data from Clinical Trials” [001-MCG-156] ([8](#)).

The standard AE analyses will be based on the number of subjects with AEs (and not on the number of AEs).

For analysis multiple AE occurrence data on the CRF will be collapsed into an AE provided that all of the following applies:

- All AE attributes are identical (LLT, intensity, action taken, therapy required, seriousness, reason for seriousness, relationship, outcome, AE of special interest)
- The occurrences were time-overlapping or time-adjacent (time-adjacency of 2 occurrences is given if the second occurrence started within one hour after end of the first occurrence).

For further details on summarization of AE data, please refer to [001-MCG-156] ([8.4](#)).

Section 5.2.2.1 of the CTP: *The following are considered as AESIs:*

- Hepatic injury

A hepatic injury is defined by the following alterations of hepatic laboratory parameters:

- *an elevation of AST and/or ALT ≥ 3 -fold ULN combined with an elevation of total bilirubin ≥ 2 -fold ULN measured in the same blood sample, and/or*
- *aminotransferase (ALT, and/or AST) elevations ≥ 10 fold ULN*

These lab findings constitute a hepatic injury alert and the patients showing these lab abnormalities need to be followed up according to the 'DILI checklist' provided in the ISF. In case of clinical symptoms of hepatic injury (icterus, unexplained encephalopathy, unexplained coagulopathy, right upper quadrant abdominal pain, etc.) without lab results (ALT, AST, total bilirubin) available, the Investigator should make sure these parameters are analysed, if necessary in an unscheduled blood test. Should the results meet the criteria of hepatic injury alert, the procedures described in the DILI checklist should be followed.

The analysis of adverse events will be based on the concept of treatment emergent adverse events.

Section 5.2.2.2 of the CTP:

The REP refers to the oral drug administration. The REP of the BI 409306 (13-C/15-N) is considered to be negligible. Therefore, all AEs that occur through the treatment phase and throughout the REP will be considered as on treatment (without differentiation of intravenous or oral administration) [...].

All adverse events occurring before first drug administration will be assigned to 'screening', those between intake of trial medication and end of the 24-hour REP will be assigned to treatment ('on treatment'). AEs occurring after the REP but prior to termination date will be assigned to 'follow-up'.

For more detail see the TSAP ADS plan.

According to ICH E3 (9), AEs classified as 'other significant' need to be reported and will include those non-serious and non-significant adverse events with

- (i) 'action taken = discontinuation' or 'action taken = reduced', or
- (ii) marked haematological and other lab abnormalities or lead to significant concomitant therapy as identified by the Clinical Monitor/Investigator at the Report Planning Meeting.

An overall summary of AEs (including AESIs) will be presented.

The frequency of subjects with AEs will be summarised by treatment (BI tab + iv), primary system organ class (SOC) and preferred term (PT). Separate tables will be provided for subjects with other significant AEs according to ICH E3 (9), for subjects with serious AEs, for subjects with drug-related AEs, for subjects with drug related serious adverse events and for subjects with AESIs.

The SOC and PTs will be sorted by frequency. The MedDRA version number will be displayed as a footnote in the respective output.

In addition, frequencies of subjects with non-serious AEs that had an incidence of > 5% for at least one treatment will be summarised by treatment, primary SOC and PT.

For disclosure of adverse events on EudraCT, additional information not included in a standard AE analysis will be performed. The following three entries will be created:

- Adverse Events per arm for disclosure on EudraCT
- Non-serious Adverse Events for disclosure on EudraCT
- Serious Adverse Events for disclosure on EudraCT

